6.4. End of Blinded Treatment Phase Visit

Once all participants have had at least 96 weeks of follow up after randomization and upon notification by Gilead, all participants will return to the study center for an end of blinded treatment phase visit (may coincide with their next scheduled study visit).

Participants who do not participate in the OL phase will discontinue their blinded study drug and will return for a 30-Day Follow-Up visit following the end of blinded treatment phase visit.

The following will be performed at the end of blinded treatment phase visit:

- Targeted (symptom directed) physical examination
- Review of AEs and changes in concomitant medications, including assessment of whether any STIs were diagnosed and any treatments were received since the last visit
- When clinically indicated, vital signs measurement (blood pressure, pulse, respiration rate, and temperature)
- Weight
- STI testing. Participants who test positive for any STI will be treated in accordance with local STI guidelines.
 - Genital, rectal, and pharyngeal examination as appropriate
 - Pharyngeal and rectal swabs for gonorrhea and chlamydia (per local lab). Swabs may be self-administered by the participant at the discretion of the investigator.
 - Urine sample for gonorrhea and chlamydia (per central lab)
 - Blood sample for syphilis testing (per local lab)
- Fourth generation rapid HIV-1 Ag/Ab or third generation rapid HIV-1 Ab test (**not done for participants who acquire HIV**)
 - If the result for rapid testing is positive, a retest will be completed. If the retest is positive, an HIV-1 RNA by PCR test and sample collection for possible genotypic resistance testing will be completed.

- Urine collection for urinalysis, urine proteins, urine chemistry (uric acid, phosphate, and creatinine), and sample storage
- Blood sample collection for the following central laboratory analyses:
 - Hematology profile: CBC with differential and platelet count
 - Chemistry profile: alkaline phosphatase, AST, ALT, GGT, total bilirubin, direct and indirect bilirubin, total protein, albumin, LDH, bicarbonate, BUN, calcium, chloride, creatinine, glucose, phosphorus, magnesium, potassium, sodium, uric acid, and amylase (reflex lipase testing is performed in participants with total amylase $> 1.5 \times$ ULN)
 - Estimated GFR according to the Cockcroft-Gault formula for creatinine clearance
 - HIV-1 Ab/Ag (not done for participants who acquire HIV)

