## 1. INTRODUCTION

The primary analysis of HIV-1 pre-exposure prophylaxis (PrEP) in Study GS-US-412-2055 has been done (clinical study report [CSR] date: 25 March 2019) after all subjects had either a minimum follow-up of 48 weeks and at least 50% of the subjects had 96 weeks of follow-up after randomization or prematurely discontinued from the study. This statistical analysis plan (SAP) describes the statistical analysis methods and data presentations to be used in tables, figures, and listings (TFLs) of the end of blinded phase analysis, which will be performed when all subjects have either completed the end of blinded treatment visit or prematurely discontinued from the study. The end of blinded phase is also the end of randomized phase, and we will use the phrases double-blinded (DB) phase and randomized phase interchangeably. Although the study was unblinded for the primary analysis, blind was maintained at the participant, investigator and operational staff at Gilead.

This SAP is based on the study protocol amendment 5 dated 5 September 2018, the electronic case report form (eCRF), data transfers for laboratory tests, the Computer-Assisted Self-Interview (CASI) questionnaire, and dual energy x-ray absorptiometry (DXA). The SAP will be finalized before database finalization for the final unblinding of the end of blinded phase analysis.

[figure not shown]

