# 4.1.2. Subject Disposition

The summary of subject disposition will be provided by treatment group and overall for all screened subjects. This summary will include the number of subjects screened, screen failure subjects who were not randomized, subjects who met all eligibility criteria and were not randomized, subjects randomized but never treated, subjects who were HIV positive at screening, subjects in the Safety Analysis Set, and subjects in the FAS, as applicable.

In addition, the number and percentage of the subjects in the following categories will be summarized:

- Still on study drug in the DB phase, if applicable
- Completing study drug in the DB phase
- Prematurely discontinuing study drug in the DB phase (with summary of reasons for discontinuing study drug)
- Still on study in the DB phase, if applicable
- Completing study in the DB phase (see Appendix 11)
- Prematurely discontinuing from study in the DB phase (with summary of reasons for discontinuing study)
- Entering in the OLE phase

The denominator for the percentages of subjects in each category will be the number of subjects in the Safety Analysis Set. Separate summaries of subject disposition in each category by treatment group and overall will include subjects in the Hip or Spine DXA Analysis Sets.

No inferential statistics will be generated. A data listing of reasons for premature study drug/study discontinuation will be provided.

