## **Appendix 12. Programming Specification**

- 1) AGE calculated as follows:
  - a) AGE (years) is calculated from the number of days between the date of birth (DOB) and Day 1 (first dose date),
  - b) Use the SAS INTCK function to determine the number of "1st-of-month days" (ie, January 1st, February 1st, March 1st) between DOB and Day 1 (inclusive),
  - c) Divide the result in (b) by 12,
  - d) AGE the integer of the result in (c),
  - e) If the DOB and Day 1 have the month in common and the birthday is later in the month than the date of Study Day 1, then subtract one from the AGE result above.
- 2) For subjects randomized and never dosed with study drug, age will be calculated from the date of randomization.
- 3) All screened subjects refer to all subjects who are screened (ie, with nonmissing screening date) and have a screening number. For summaries, the same subject is counted only once. DOB and other demographic information such as sex, race, ethnicity, country, and initials will be used to identify unique screened subjects.
- 4) Screen failure subjects are the subjects who are screened and answered "No" for any inclusion criteria or "Yes" for any exclusion criteria regardless of which version of protocol the subject was consent to.
- 5) Subjects in the randomized analysis set are defined as subjects randomized into the study. IXRSRAND is the source to determine whether the subject is randomized (ie, subject with nonmissing RGMNDTN in the IXRSRAND dataset) and confirmed by the eCRF ENROLL dataset (ie, ENROLLYN "Yes" in ENROLL dataset).
- 6) Randomized treatment (ie, TRT01P in ADSL) is derived from IXRSRAND, while actual treatment received (ie, TRT01A in ADSL) is assigned as the randomized treatment if subject took at least 1 dose of study drug and assigned as blank if subject never dosed.
- 7) In disposition table, the reasons for premature discontinuation are displayed in the order as they appear on the eCRF.

- 8) Only 1 study completion form is collected for the entire study. Therefore, study disposition in the DB phase of the study is defined as follows for dosed subjects:
  - f) Subjects who completed study in the DB phase are defined as follows:
    - i) Open-label entry eCRF marked as "Yes", OR
    - ii) Open-label phase first dose date is present, OR
    - iii) Study completion form is marked as "Yes".

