  - g) Subjects who are ongoing in the DB phase of the study is defined as subjects who have not entered the OLE phase of the study, DB phase study drug completion form is marked as "N" or missing, and study completion form is also missing.
  - h) Subjects not meeting (a) and (b) above will be the subjects who discontinued study in the DB phase of the study.
- 9) Body mass index (BMI) will be calculated only at baseline as follows:
- BMI (weight [kg]) / (height [meters])

Baseline height and weight will be used for this calculation.

- 10) For summaries using the PK Case-Control Analysis Set by HIV infection cases versus uninfected matched controls, if one subject serves as both as case and control, this subject will be summarized under both the HIV infection case and uninfected matched control columns.
- 11) SAS codes for the treatment comparison for demographics and baseline characteristics tables.
  - i) CMH test for nominal variable (Y), the p-value from general association test should be used for nominal variable (including race, ethnicity, education, employment, sexuality, number of subjects with a syphilis diagnosis, circumcision, geography, and dichotomous variables):

```
proc freq data=adsl;
   tables trtgrp * Y /cmh /*general association test*/
run;
```

j) CMH test for ordinal variable (Y), the p-value from row mean score test should be used for ordinal variable (including the number of subjects with each STI lab test result type, ongoing relationship, AUDIT questions or total score, proteinuria toxicity grade by urinalysis and categorical summaries of any continuous variables like age, adherence rate or number of partners):

```
proc freq data=adsl;
   tables trtgrp * Y / cmh2 score=modridit; /*row mean score test*/
run:
```

k) Wilcoxon rank sum test for continuous variable (Y), the p-value from the normal approximation 2-sided test should be used for continuous variable:

```
proc npar1way wilcoxon data=adsl;
  class trtgrp;
  var Y;
run;
```

1) Van Elteren test stratified by baseline F/TDF for PrEP:

```
proc freq data=test;
table bftdf*trt*outcome/cmh2 scores=modridit;
run;
```

Where bftdf is baseline F/TDF for PrEP (yes or no), trt is treatment, and outcome is the % change or change from baseline depending on endpoint of interest. Please report p-value from row mean scores differ.

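### SAP Appendix 12 item 8 counts a participant who finished blinded drug, did not enter open label and has no study completion form yet as a study discontinuation

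*SAP*

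**What the plan says.** SAP Section 4.1.2 plans a disposition table for the double-blind (DB) phase. It has separate rows for study drug and for study participation. The study rows are still on study (if applicable), completed, and "Prematurely discontinuing from study in the DB phase (with summary of reasons for discontinuing study". Percentages use the Safety Analysis Set.

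The derivation is in SAP Appendix 12, item 8. It starts from the fact that "Only 1 study completion form is collected for the entire study", so DB-phase status has to be inferred:

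- **Completed, 8(f):** open-label entry form marked Yes, or an open-label first dose date, or the study completion form marked Yes.
- **Ongoing, 8(g):** participants who "have not entered the OLE phase of the study, DB phase study drug completion form is marked as" N or missing, and whose study completion form is also missing.
- **Discontinued, 8(h):** everyone else. "Subjects not meeting (a) and (b) above will be the subjects who discontinued study in the DB phase of the study". The letters (a) and (b) can only mean the two preceding sub-items, printed as (f) and (g). Sub-item letters run on across items in this appendix, and nothing turns on that.

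Two other provisions matter. Under Protocol Section 6.4, participants who do not take part in the open-label phase stop blinded drug and "will return for a 30-Day Follow-Up visit following the end of blinded treatment phase visit". Protocol Section 3.2 and SAP Section 1.2 say the same. Under SAP Section 1, the analysis is to be "performed when all subjects have either completed the end of blinded treatment visit or prematurely discontinued from the study", and SAP Section 2.3 repeats that trigger. Neither SAP passage makes the analysis wait for the 30-day follow-up.

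**The concern.** A remainder class is safe only if the other classes catch everyone who does not belong in it. Here the ongoing class is narrowed by a condition on the drug form, which says nothing about whether a person is still in the study. That condition removes those who took blinded drug to the end.

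The protocol creates a period in which this matters. A participant who declines open label has finished treatment but still owes a visit. If the single study form is filed after that visit, there is an interval with the drug form at Yes and the study form missing. Anyone in that interval at the data cut would be reported as a premature study discontinuation, and the accompanying summary and listing of reasons would have no reason to show, because the form does not yet exist. Readers use these rows to judge retention, so a rule that can put treatment completers among the dropouts should be corrected.

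**Working it through.** The SAP states no figure to reproduce. The check is to apply 8(f)–(h) to every combination of the two forms for a dosed participant with no open-label entry and no open-label dose. For such a person the first two routes to completed are closed, and only the study form can meet 8(f).

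| Drug completion form | Study completion form | Class under 8(f)–(h) | Class using the study form alone |
|---|---|---|---|
| Yes | Yes | completed | completed |
| Yes | No | discontinued | discontinued |
| **Yes** | **missing** | **discontinued** | **still on study** |
| N | Yes | completed | completed |
| N | No | discontinued | discontinued |
| N | missing | ongoing | still on study |
| missing | Yes | completed | completed |
| missing | No | discontinued | discontinued |
| missing | missing | ongoing | still on study |

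One cell is wrong. With the study form missing, a participant who stopped drug early (N) is ongoing, while one who completed drug (Yes) is discontinued. No other passage in the SAP redirects that cell.

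**Can the cell be occupied?** Protocol Section 6.7.3 puts the follow-up at 30 days after stopping study drug, with up to 14 more days allowed, so as late as 30 + 14 = 44 days. The analysis trigger is the end-of-blinded visit. The documents do not say when the study completion form is filed. Filing after the follow-up is an inference; it fits one form for the whole study, and it fits SAP Section 3.8.1, where the last study date includes the 30-day visit for participants with a completed or discontinued status on that form. The documents also give no data-cut date. If forms were filed on the day of the follow-up and the cut came at least 44 days after the last decliner's final dose, timely follow-ups would leave the cell empty.

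**Scale.** Let k be the number of participants in that cell at the cut. The discontinued row is too high by k, and the still-on-study row too low by k. With the Safety Analysis Set of 5387 (SAP Appendix 3), the error in percentage points is 100 × k / 5387, both arms together:

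- k = 0: 0
- k = 10: 0.19
- k = 50: 0.93
- k = 100: 1.86
- k = 250: 4.64

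One percentage point corresponds to 5387 / 100 ≈ 54 participants. These values of k are illustrations only.

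**The case against.** The strongest reply is that the cell may be empty. The trigger in SAP Sections 1 and 2.3 is a minimum condition, not a date on which data are frozen, and SAP Section 1 refers to database finalization as a separate step. The SAP also expects 30-day follow-up data in this analysis: the last at-risk date in Section 3.8.1 and the time at risk in Section 6.2.3 both allow for that visit. Protocol Section 9.1.6 requires the investigator to review and sign the forms before any interim or final time point. All of this stands. It makes a cut with no lag less likely, but it does not establish that every study form is in. The SAP itself keeps a still-on-study row and, in Appendix 12, a rule for imputing the last study date of ongoing participants.

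A reader might go further than the documents allow in three ways:

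- **That discontinuation is overstated by a known amount.** It is not known. Any figure needs the share who decline open label, the spread of their last visits and the lag to the cut, and none of these is given.
- **That completion is understated.** On the protocol's own terms these people still owe a visit, so the row that loses them is still on study, not completed.
- **That the non-inferiority result is touched.** It is not. Person-time in SAP Section 6.2.3 ends at HIV diagnosis or the last HIV test, not at a disposition class. The primary analysis was already done and is not repeated. The study-drug rows are separate, and the disposition table carries no inferential statistics.

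**Conclusion.** The point holds as a defect in a derivation rule, conditional in its effect. As written, 8(g)–(h) class a participant with completed blinded drug, no open-label entry and a missing study completion form as having discontinued the study, while someone who stopped drug early with the same missing form is ongoing. If any such forms are pending at the cut, the Section 4.1.2 table would overstate premature study discontinuation, with no recorded reason, and understate those still on study by the same count.

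The conclusion about the rule rests on the text alone. The conclusion about the table rests on two things the documents leave open: that the form follows the 30-day visit, and that the cut precedes some of those forms. The size is therefore undetermined and may be zero. The effect is confined to a descriptive table, so this is a minor correction, worth making because a prespecified rule should not be right only when the cut happens to be late.

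**What to change.** For dosed participants who have not entered open label (no open-label entry and no open-label dose), let the study completion form alone decide: Yes = completed, No = discontinued, missing = still on study. In the text of Appendix 12 item 8:

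- **8(g):** delete the condition on the drug completion form.
- **8(h):** replace the remainder rule with study completion form marked No.

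As the last column of the table above shows, this covers every combination without overlap and changes only the faulty cell.

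Do not instead add completed blinded drug as a fourth route to completion in 8(f). That would also class as completed anyone with drug form Yes and study form No, for example a participant lost before the follow-up, and so override an explicit No.

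While editing, correct the pointer in Section 4.1.2: it sends the reader to Appendix 11 for the definition of completing the study, but Appendix 11 is selected medical history and the rule is in Appendix 12. The cost is two lines of SAP text and the matching program change, with no new data.

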# Last Dose Date Imputation for Subjects who are Ongoing on Study Drug Subjects (for the purpose of duration of exposure)

Last dose date is not defined for subjects still on study drug in SAP. However, for the calculation of the duration of exposure to study drug, for subjects who have not permanently discontinued study drug at the time of the data cut date, the estimated last dose date will be the maximum of nonmissing study drug start dates and end dates, the clinic visit dates, and the laboratory visit dates excluding the date of 30-day follow-up visit.

b) Last Study Date is the latest of the study drug start dates and end dates, the clinic visit dates, and the laboratory visit dates, including the 30-day follow-up visit date, for subjects who prematurely discontinued study or who completed study according to the Study Completion eCRF. If study drug start dates or end date is partially missing (ie, only year and month are known), the day will be imputed as 15 for the purpose of this analysis.

If subject died and the death date is complete (ie, not partial date) and before the imputed last study date, the complete death date should be used as the imputed last study date.

# **Last Study Date Imputation for Ongoing Subjects**

Statistical Analysis Plan – End of Blinded Treatment Phase Analysis

Last study date is not defined for subjects still on study in SAP. However, for programing purposes, the latest of study drug start dates and end dates, the clinic visit dates, and the laboratory visit dates, including the 30-day follow-up visit date, will be used to impute the last study date for subjects still on study.

- 15) For the purpose of calculating study drug interruptions, the start date of an interruption is the previous study drug administration end date + 1 day and end date of an interruption is the next time consecutive study drug administration start date 1 day.
- 16) Efficacy analyses:

Covance HIV Laboratory Tests

HIV Test Description	HIV-1 Positive results	HIV-1 Negative results	LBTEST	LBTESTCD
HIV-1/HIV-2 screening test (Ag/Ab - 4 th generation)	Repeatedly Reactive	Non-reactive	'HIV 1/2 Ag/Ab Screen, Siemens'	CNT449
HIV-1/HIV-2 screening test (Ab - 3 rd generation)	Repeatedly Reactive	Non-reactive	'Ab to HIV Type1/Type2-QT'	CNT425
HIV-1/HIV-2 Discrimination Ab test	HIV-1 Positive, HIV2 Pos-HIV1 Cross-reactive, HIV Positive Untypable, 'HIV-2 positive, HIV-1 cross reactive'	HIV Negative, HIV-1 Indeterminate, HIV-2 Indeterminate, HIV Indeterminate, HIV-2 Positive, HIV Antibody Negative	'HIV Ab Interpretation, Geenius'	IMT1948
HIV-1 Qualitative, RNA	Positive	Negative, or Invalid	'HIV-1 RNA Qual,EDTApl-335'	ORT11277
HIV-1 Quantitative RNA	<20 cp/mL HIV-1 RNA Detected or numeric value	No HIV-1 RNA detected,	'HIV RNA TaqMan-2.0-EDTA-CL'	GET1816

a) For the primary efficacy analysis, the HIV infection incidence rate between F/TAF and F/TDF and its 95.003% or 95% CIs are calculated using the rate ratio method. To test superiority, the p-value from 2-sided test should be used, where trtgrp is the treatment, sero is the number of HIV infection events and ln is the natural log of the summation of all subjects' person years follow-up time. The following SAS code will be used to compute the HIV infection incidence rate and p-value.

```
data rate;
  input ptyr sero trtgrp$ ptvd $;
  ln = log(ptyr);
  datalines;
  1500  17  FTAF Y
  1500  16  FTDF Y
  3500  35  FTAF N
  3500  34  FTDF N;
proc genmod data=rate;
  class trtgrp (ref='FTDF');
  model sero = trtgrp / dist=poisson link=log offset=ln;
  lsmeans trtgrp / ilink diff exp cl alpha=0.04997;
run;
```

b) For a sensitivity analysis, the HIV infection incidence rate between F/TAF and F/TDF and its 95% exact CIs are calculated using the rate differences method. All references to 95% exact CIs are calculated using the method proposed by Ulm. The following SAS code will be used:

```
/*Hybrid CI*/
data test;
   alpha=0.025;
   zval = quantile("Normal", alpha);
   x1=42; *Number of HIV Infections in F/TAF arm;
   x2=101; *Number of HIV Infections in F/TDF arm;
   f1=500; *Total Person Years Follow Up in F/TAF arm;
   f2=400; *Total Person Years Follow Up in F/TDF arm;
    hat1 = x1/f1;
    hat2 = x2/f2;
    diff = hat1 hat2;
      /*Rate Difference: Hybrid CI*/
   11 quantile("CHISQ", alpha, 2*x1)/(2*f1); *Ulm lower exact CI;
   u1 quantile("CHISQ", 1-alpha, 2*x1+2)/(2*f1); *Ulm upper exact CI;
   12 quantile("CHISQ", alpha, 2*x2)/(2*f2); *Ulm lower exact CI;
   u2 quantile("CHISQ", 1-alpha, 2*x2+2)/(2*f2); *Ulm upper exact CI;
   hybriddifflower hat1 - hat2 - sqrt((hat1 - 11)**2 + (u2 - hat2)**2);
*Lower CI of Rate Difference (F/TAF-F/TDF);
   hybriddiffupper hat1 - hat2 + sqrt((hat1 - u1)**2 + (12 - hat2)**2);
*Upper CI of Rate Difference (F/TAF-F/TDF);
run;
```

d) The FAS and PP populations are based on HIV lab test results from either Covance or the Rapid HIV-1/2 Result (LB-HIVDX) eCRF, excluding the Other Local Labs eCRF.

